# **10.3.** Appendix 3: Adverse Events: Definitions and Procedures for Recording, Evaluating, Follow-Up, and Reporting

### **10.3.1. Definition of AE**

#### **AE Definition**

- An AE is any untoward medical occurrence in a patient or clinical study participant, temporally associated with the use of study intervention, whether or not considered related to the study intervention.
- Note: An AE can therefore be any unfavorable and unintended sign (including an abnormal laboratory finding), symptom, or disease (new or exacerbated) temporally associated with the use of study intervention.

## **Events** Meeting the AE Definition

- Any abnormal laboratory test results (hematology, clinical chemistry, or urinalysis) or other safety assessments (eg, ECG, radiological scans, vital sign measurements), including those that worsen from baseline, considered clinically significant in the medical and scientific judgment of the investigator. Any abnormal laboratory test results that meet any of the conditions below must be recorded as an AE:
  - Is associated with accompanying symptoms.
  - Requires additional diagnostic testing or medical/surgical intervention.
  - Leads to a change in study dosing (outside of any protocol-specified dose adjustments) or discontinuation from the study, significant additional concomitant drug treatment, or other therapy.
- Exacerbation of a chronic or intermittent preexisting condition, including either an increase in frequency and/or intensity of the condition.
- New condition detected or diagnosed after study intervention administration, even though it may have been present before the start of the study.
- Signs, symptoms, or the clinical sequelae of a suspected drug-drug interaction.
- Signs, symptoms, or the clinical sequelae of a suspected overdose of either study intervention or a concomitant medication. Overdose per se will not be reported as an AE or SAE unless it is an intentional overdose taken with possible suicidal/self-harming intent. Such overdoses should be reported regardless of sequelae.

## **Events NOT** Meeting the AE Definition

- Any clinically significant abnormal laboratory findings or other abnormal safety assessments that are associated with the underlying disease, unless judged by the investigator to be more severe than expected for the participant's condition.
- The disease/disorder being studied or expected progression, signs, or symptoms of the disease/disorder being studied, unless more severe than expected for the participant's condition.
- Medical or surgical procedure (eg, endoscopy, appendectomy): the condition that leads to the procedure is the AE.
- Situations in which an untoward medical occurrence did not occur (social and/or convenience admission to a hospital).
- Anticipated day-to-day fluctuations of preexisting disease(s) or condition(s) present or detected at the start of the study that do not worsen.

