# **8.3.7.** Disease-Related Events and/or Disease-Related Outcomes Not Qualifying as AEs or SAEs

Not applicable.

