### 8.3.8.1. Lack of Efficacy

The investigator must report signs, symptoms, and/or clinical sequelae resulting from lack of efficacy. Lack of efficacy or failure of expected pharmacological action is reportable to Pfizer Safety **only if associated with an SAE**.

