#### **10.3.2. Definition of an SAE**

An SAE is defined as any untoward medical occurrence that, at any dose, meets one or more of the criteria listed below:

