#### c. Requires inpatient hospitalization or prolongation of existing hospitalization

In general, hospitalization signifies that the participant has been admitted (usually involving at least an overnight stay) at the hospital or emergency ward for observation and/or treatment that would not have been appropriate in the physician's office or outpatient setting. Complications that occur during hospitalization are AEs. If a complication prolongs hospitalization or fulfills any other serious criteria, the event is serious. When in doubt as to whether "hospitalization" occurred or was necessary, the AE should be considered serious.

Hospitalization for elective treatment of a preexisting condition that did not worsen from baseline is not considered an AE.

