3. ENDPOINTS AND BASELINE VARIABLES: DEFINITIONS AND CONVENTIONS

3.1. Primary Endpoint

• Proportion of participants with COVID-19 related hospitalization or death from any cause through Day 28.

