6.2.2. Incidence of Treatment Emergent Adverse Events (TEAEs)

The incidence of TEAEs will be summarized by treatment group, by system organ class (SOC) and preferred term (PT) using the SAS population.

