6.2.3. Incidence of SAEs and AEs Leading to Discontinuations

The incidence of SAEs and AEs leading to discontinuation will be summarized by treatment group using the SAS population.

6.2.4. Time (days) to Sustained Alleviation and Time to Resolution of Targeted COVID-19 Sign/Symptoms through Day 28

The time (days) to sustained alleviation and time to resolution will be defined for all targeted COVID-19 associated symptoms based on self-assessment.

Sustained alleviation of all targeted COVID-19 signs/symptoms is defined as the event occurring on the first of 4 consecutive days when all symptoms scored as moderate or severe at study entry are scored as mild or absent AND all symptoms scored mild or absent at study entry are scored as absent. The first day of the 4 consecutive-day period will be considered the First Event Date.

Sustained resolution is defined as when all targeted symptoms are scored as absent for 4 consecutive days. The first day of the 4 consecutive-day period will be considered the First Event Date.

For symptoms with no reported severity in baseline, the symptom will have to be absent in order to be counted as sustained alleviated/resolved (missing severity at baseline will be treated as mild).

Day 25 is the last possible day the symptom alleviation and resolution endpoints can be achieved (definition includes data from the subsequent three days) and Day 28 is the last day participants report their daily signs and symptoms.

The time to sustained symptom alleviation/resolution for the purpose of this study is defined as:

PFIZER CONFIDENTIAL
Page 23

- For a participant with sustained symptom alleviation/resolution (event), time to event will be calculated as (First Event Date) (First Dose Date) +1.
- For a participant that either completes Day 28 of the study or discontinues from the study before Day 28 without sustained symptom alleviation/resolution (censored), censoring date will be at the last date on which symptom alleviation/resolution is assessed, and time will be calculated as (Censoring Date) (First Dose Date) +1 or Day 25 whichever occurs first.

The decision to require 4 consecutive days with all targeted symptoms absent was based on exploratory analyses of data from the ACTIV-2/A5401 study, which suggested that this choice (rather than requiring fewer consecutive days) better captured sustained symptom resolution with low probability of subsequent relapse.

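### The protocol leaves open whether a COVID-19 hospitalization is recorded as an SAE, and the SAP does not separate COVID-19 progression in its SAE summary

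*Protocol*

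**What the plan says.** The protocol touches on COVID-19 progression as a safety event in four places.

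- Section 10.3.1 (Appendix 3), under events that do not meet the AE definition, lists "The disease/disorder being studied or expected progression, signs, or symptoms of the disease/disorder being studied, unless more severe than expected for the participant's condition".
- Section 8.3.7 is headed "Disease-Related Events and/or Disease-Related Outcomes Not Qualifying as AEs or SAEs". Its whole content is that it does not apply.
- Section 8.3.8.1 states: "The investigator must report signs, symptoms, and/or clinical sequelae resulting from lack of efficacy". It adds that lack of efficacy goes to the sponsor's safety group only when an SAE is associated with it.
- Section 10.3.2 states: "An SAE is defined as any untoward medical occurrence that, at any dose, meets one or more of the criteria listed below". Death is the first criterion and the third is "Requires inpatient hospitalization or prolongation of existing hospitalization". No criterion exempts the study disease or events that count towards the primary endpoint.

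The primary endpoint (SAP 3.1) is "Proportion of participants with COVID-19 related hospitalization or death from any cause through Day 28". SAE incidence is both a secondary endpoint (SAP 3.2) and a safety endpoint (SAP 3.6). SAP 6.2.3 states: "The incidence of SAEs and AEs leading to discontinuation will be summarized by treatment group using the SAS population". SAP 6.2.2 gives more detail for TEAEs: "The incidence of TEAEs will be summarized by treatment group, by system organ class (SOC) and preferred term (PT) using the SAS population". SAP 6.6 and 6.6.1 add standard sponsor tables and listings, MedDRA coding and a pre-specified AESI list. The SAP's own AE definition (3.6.1) has no exclusion for the study disease. Neither document describes an SAE, TEAE or fatal-event summary that leaves out COVID-19.

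**The concern.** A participant admitted for worsening COVID-19 counts in the primary analysis. Whether the same admission also counts as an SAE depends on the section that the investigator relies on. Under 10.3.1, progression judged to be expected is not an AE. Under 8.3.8.1 and 10.3.2 read on their own, the admission is reportable and serious. The exception in 10.3.1 gives no usable threshold: participants are enrolled because they are at raised risk of progression (inclusion criterion 4), so an admission can in good faith be called expected or worse than expected.

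The meaning of a stated secondary endpoint is at stake. If every such event is recorded, an effective drug lowers its own SAE rate through efficacy, and this can offset an excess of other SAEs in the overall figure. If none is recorded, the rate describes other harm only. If sites differ, the overall rate mixes the two in unknown proportion. Sites also need one rule for a practical reason: Section 8.3.1.1 requires every SAE to be reported within 24 hours.

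**Working it through.** **Inputs.** Protocol 9.5 and SAP 2.3 give 7% events on placebo, a 3.5-point difference (so 3.5% on active), 90% power, 2-sided 5%, 1717 participants for the primary analysis and about 3000 in total. Allocation is 1:1 (Protocol 4.1). The documents give no expected SAE rate, so everything about other SAEs below is assumed.

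**1. Check of the design rates.** With p1 = 0.07, p2 = 0.035 and mean 0.0525:

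n per arm = [1.960·√(2 × 0.0525 × 0.9475) + 1.282·√(0.07 × 0.93 + 0.035 × 0.965)]² / 0.035² = (0.6182 + 0.4030)² / 0.001225 = 851.3, rounded up to 852.

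That is 1704 in total. The planned 1717 is within 1% of this and gives 90.2% power. The total follows from the 20% mAb share, the 25% late-onset share and 5% dropout: 1717 / (0.80 × 0.75 × 0.95) = 3012, about 3000. So 7% and 3.5% are the rates on which the plan rests.

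**2. Set-up.** Let b be the incidence of other SAEs on placebo, h the excess of other SAEs on active, and f the share of COVID-19 hospitalizations and deaths recorded as SAEs. Take f as equal in both arms, since recording is blinded, and assume that no participant has both kinds of event. In percentage points:

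- placebo SAE rate = b + 7.0f
- active SAE rate = b + h + 3.5f
- active minus placebo = h − 3.5f, so b cancels

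**3. Overall SAE difference (points), over a range of assumptions.**

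| f | h = 1 | h = 2 | h = 3.5 |
|---|---|---|---|
| 0 | +1.0 | +2.0 | +3.5 |
| 0.25 | +0.125 | +1.125 | +2.625 |
| 0.50 | −0.75 | +0.25 | +1.75 |
| 0.75 | −1.625 | −0.625 | +0.875 |
| 1 | −2.5 | −1.5 | 0 |

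The excess is cancelled at f = h/3.5: 1/3.5 = 0.29, 2/3.5 = 0.57 and 3.5/3.5 = 1. For example, with b = 1%, h = 1 and f = 1, the overall rates are 5.5% on active and 8.0% on placebo, while other SAEs alone are 2.0% and 1.0%.

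**4. In participants.** For the primary population, 858 × 0.07 = 60 on placebo and 858 × 0.035 = 30 on active. If the same rates held for 1500 per arm, 1500 × 0.07 = 105 and 1500 × 0.035 = 52.5. Efficacy alone would then put up to about 52 fewer participants with an SAE on active.

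**5. The safety set is wider.** SAEs are summarized in the Safety Analysis Set. It also holds mAb recipients and participants treated more than 3 days after onset, and no event rate is given for them. With a difference of d points there, the result is h − d·f. If d were half the design value (1.75, assumed), a 1-point excess would be offset at f = 1/1.75 = 0.57. If d were below 1, it would not be offset at any f.

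**6. What separation would show.** With h = 1 and 1500 per arm, a 2-sided 5% comparison of other SAEs alone would have about 62% power at b = 1% (79% at b = 0.5%, 42% at b = 2%). The plan tests no SAE difference. These figures only indicate how visible such an excess would be once separated.

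**Limits.** The 7% and 3.5% include deaths from other causes, which are treated as negligible here. The two descriptions of hospitalization also differ: more than 24 hours of acute care in 8.1.2, and usually at least overnight in 10.3.2. Endpoint events and SAEs therefore need not match one to one.

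**The case against.** The sections can be read so that they agree. Section 10.3.1 readmits events more severe than expected. Exclusion criterion 2 keeps out anyone who needs admission or is expected to within 48 hours, and the design assumes that 93% of placebo participants have no event. Admission or death is therefore arguably beyond the expected course, and so an AE under 10.3.1 and serious under 10.3.2. Section 8.2.6 applies the same test to laboratory findings, so this rule is not confined to the appendix. Section 8.3.7 may mean only that no special list of exempt events was drawn up. Section 8.3.8.1 does not declare progression to be an AE. Section 10.3.2 leans towards serious when a hospitalization is in doubt. On the analysis side, SAEs are described and are outside the testing sequence in SAP 5.1. Explicit COVID-19 terms would appear as their own preferred terms, AESIs are pre-specified, and the E-DMC sees unblinded safety data and reviews all deaths.

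Much of this stands. A reader might infer that the protocol gives two flatly opposite rules, but the exception in 10.3.1 means that a COVID-19 hospitalization could qualify under every section. The accurate description is an unresolved rule left to investigator judgment.

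The reconciling reading is nowhere stated, however. The tie-break in 10.3.2 concerns whether an admission occurred or was needed, not whether progression is an AE. The other outputs separate only in part:

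- Preferred-term rows cannot be added up to the number of participants with at least one non-COVID SAE.
- Section 2.2 of the protocol names ARDS, cardiac injury, thromboembolic events and kidney injury as complications of COVID-19, and such terms could reflect disease or drug.
- The AESI list includes raised CRP, fibrinogen and D-dimer, and 10.3.1 applies the same expectedness test to laboratory findings tied to the disease.

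**Conclusion.** The point holds as an unresolved recording rule combined with a missing split in the SAP. At the design rates, recorded COVID-19 events move the overall SAE difference by −3.5f points, with a maximum of 3.5 points in favour of active. An assumed 1-point excess of other SAEs would change sign in the overall figure at f of about 0.29. This rests on the assumed excess, no overlap between event types, equal f in the two arms, and primary-population rates that may not hold in the whole safety set.

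Two further readings are tempting but unsupported. One is that all SAEs go into a single pooled table. SAP 6.2.3 says only that they are summarized by treatment group, and the content of the standard tables is not described. The other is that drug harm would be hidden across the safety analysis. Masking is limited to the overall SAE rate, because the tables by system organ class and preferred term, the AESIs and the E-DMC review remain. No formal test result would change either.

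The change is still worth making: it gives a stated secondary endpoint a fixed meaning at little cost.

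**What to change.** **Protocol.** Reconcile 8.3.7, 8.3.8.1, 10.3.1 and 10.3.2 into one statement of whether a COVID-19 hospitalization (as defined in 8.1.2) or death is recorded as an SAE, applied at all sites. Which way the rule goes is for the sponsor to settle. The analysis needs it to be the same everywhere.

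**SAP 6.2.2, 6.2.3 and 6.6.1.** Pre-specify SAE, TEAE and fatal-event summaries by arm, by system organ class and preferred term, with and without COVID-19 and its progression terms. Fix the term list before unblinding. For any analysis after the Day 34 unblinding, the list can be set by the blinded team that SAP 7.3 keeps in place to Week 24.

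**Cost.** One protocol statement and a few extra safety tables. COVID-19 hospitalizations are already collected as medical-visit details (Protocol 8.1.2), so the split can be made even if sites have recorded SAEs differently so far. The real downside is the judgment needed on which complication terms count as COVID-19 progression. Showing both versions side by side lets the reader see how much depends on it.

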#### **10.3.2. Definition of an SAE**

An SAE is defined as any untoward medical occurrence that, at any dose, meets one or more of the criteria listed below:

#### a. Results in death

#### b. Is life-threatening

The term "life-threatening" in the definition of "serious" refers to an event in which the participant was at risk of death at the time of the event. It does not refer to an event that hypothetically might have caused death if it were more severe.

#### c. Requires inpatient hospitalization or prolongation of existing hospitalization

In general, hospitalization signifies that the participant has been admitted (usually involving at least an overnight stay) at the hospital or emergency ward for observation and/or treatment that would not have been appropriate in the physician's office or outpatient setting. Complications that occur during hospitalization are AEs. If a complication prolongs hospitalization or fulfills any other serious criteria, the event is serious. When in doubt as to whether "hospitalization" occurred or was necessary, the AE should be considered serious.

Hospitalization for elective treatment of a preexisting condition that did not worsen from baseline is not considered an AE.

#### d. Results in persistent or significant disability/incapacity

- The term disability means a substantial disruption of a person's ability to conduct normal life functions.
- This definition is not intended to include experiences of relatively minor medical significance, such as uncomplicated headache, nausea, vomiting, diarrhea, influenza, and accidental trauma (eg, sprained ankle), that may interfere with or prevent everyday life functions but do not constitute a substantial disruption.

## e. Is a congenital anomaly/birth defect

# f. Is a suspected transmission via a Pfizer product of an infectious agent, pathogenic or non-pathogenic, is considered serious.

The event may be suspected from clinical symptoms or laboratory findings indicating an infection in a participant exposed to a Pfizer product. The terms "suspected transmission" and "transmission" are considered synonymous. These cases are considered unexpected and handled as serious expedited cases by pharmacovigilance personnel. Such cases are also considered for reporting as product defects, if appropriate.

#### g. Other situations:

- Medical or scientific judgment should be exercised by the investigator in deciding whether SAE reporting is appropriate in other situations, such as significant medical events that may jeopardize the participant or may require medical or surgical intervention to prevent one of the other outcomes listed in the above definition. These events should usually be considered serious.
- Examples of such events include invasive or malignant cancers, intensive treatment in an emergency room or at home for allergic bronchospasm, blood dyscrasias or convulsions that do not result in hospitalization, or development of drug dependency or drug abuse.

Page 84

# **10.3.3. Recording/Reporting and Follow-Up of AEs and/or SAEs During the Active Collection Period**

## AE and SAE Recording/Reporting

The table below summarizes the requirements for recording AEs on the CRF and for reporting SAEs on the CT SAE Report Form to Pfizer Safety throughout the active collection period. These requirements are delineated for 3 types of events: (1) SAEs; (2) nonserious AEs; and (3) exposure to the study intervention under study during pregnancy or breastfeeding, and occupational exposure.

It should be noted that the CT SAE Report Form for reporting of SAE information is not the same as the AE page of the CRF. When the same data are collected, the forms must be completed in a consistent manner. AEs should be recorded using concise medical terminology and the same AE term should be used on both the CRF and the CT SAE Report Form for reporting of SAE information.

Safety Event	Recorded on the CRF	Reported on the CT SAE Report Form to Pfizer Safety Within 24 Hours of Awareness
SAE	All	All
Nonserious AE	All	None
Exposure to the study intervention under study during pregnancy or breastfeeding,	All AEs or SAEs associated with exposure during pregnancy or breastfeeding	All instances of EDP are reported (whether or not there is an associated SAE)*
	Note: Instances of EDP or EDB not associated with an AE or SAE are not captured in the CRF.	All instances of EDB are reported (whether or not there is an associated SAE). **
Environmental or occupational exposure to the product under study to a non-participant (not involving EDP or EDB).	None. Exposure to a study non-participant is not collected on the CRF.	The exposure (whether or not there is an associated AE or SAE) must be reported.***

- \* **EDP** (with or without an associated AE or SAE): any pregnancy information is reported to Pfizer Safety using CT SAE Report Form and EDP Supplemental Form; if the EDP is associated with an SAE, then the SAE is reported to Pfizer Safety using the CT SAE Report Form.
- \*\* **EDB** is reported to Pfizer Safety using the CT SAE Report Form which would also include details of any SAE that might be associated with the EDB.
- \*\*\* Environmental or Occupational exposure: AEs or SAEs associated with occupational exposure are reported to Pfizer Safety using the CT SAE Report Form.
- When an AE or SAE occurs, it is the responsibility of the investigator to review all documentation (eg, hospital progress notes, laboratory reports, and diagnostic reports) related to the event.
- The investigator will then record all relevant AE or SAE information in the CRF.
- It is **not** acceptable for the investigator to send photocopies of the participant's medical records to Pfizer Safety in lieu of completion of the CT SAE Report Form/AE or SAE CRF page.
- There may be instances when copies of medical records for certain cases are requested by Pfizer Safety. In this case, all participant identifiers, with the exception of the participant number, will be redacted on the copies of the medical records before submission to Pfizer Safety.
- The investigator will attempt to establish a diagnosis of the event based on signs, symptoms, and/or other clinical information. Whenever possible, the diagnosis (not the individual signs/symptoms) will be documented as the AE or SAE.

#### **Assessment of Intensity**

An event is defined as "serious" when it meets at least 1 of the predefined outcomes as described in the definition of an SAE, NOT when it is rated as severe.

The investigator will make an assessment of intensity for each AE and SAE reported during the study and assign it to 1 of the following categories, which are based on the Division of AIDS (DAIDS) Table for Grading the Severity of Adult and Pediatric Adverse Events, version 2.1 (July 2017):

GRADE	Clinical Description of Severity
1	MILD adverse event
2	MODERATE adverse event
3	SEVERE adverse event
4	POTENTIALLY LIFE-THREATENING event
5	DEATH RELATED TO adverse event

An event is defined as "serious" when it meets at least 1 of the predefined outcomes as described in the definition of an SAE, NOT when it is rated as severe.

